1.0 Study Summary

Study Title	Pilot feasibility study of dynamic contrast-enhanced fluorescence imaging to guide total shoulder arthroplasty approach
Study Design	Cross sectional study
Primary Objective	To evaluate the feasibility of open wide-field imaging of indocyanine green ingress and egress during total shoulder arthroplasty.
Secondary Objective(s)	To characterize the relationship between tissue perfusion measured with DCE-FI and different approaches and techniques used in total shoulder arthroplasty.
Research Intervention(s)/Investigational Agent(s)	Assignment of research participants to subscapularis peel or tenotomy techniques utilized during total shoulder arthroplasty surgical approach. Indocyanine Green (ICG) indicated for soft-tissue perfusion assessment
IND/IDE #	N/A
Study Population	Patients who are undergoing open surgery for shoulder arthroplasty
Sample Size	10 patients
Study Duration for individual participants	4-6 weeks
Study Specific Abbreviations/Definitions	AIF: arterial input function CDC: Centers for Disease Control and Prevention CRF: Case Report Forms DCE-FA: Dynamic Contrast Enhanced Fluorescence Arthroscopy DCE-FI: Dynamic Contrast Enhanced Fluorescence Imaging DoD: US Department of Defense D-HH: Dartmouth-Hitchcock Health DHMC: Dartmouth Hitchcock Medical Center FI: fluorescence imaging GCP: Good Clinical Practice GFR: glomerular filtration rate HRPP: Human Research Protection Program ICG: Indocyanine Green NSF: nephrogenic sclerosing fibrosis PDD: Pulse Dye Densitometer ROI: Region of interest SSI: Surgical Site Infection

PROTOCOL TITLE: Pilot feasibility study of dynamic contrast-enhanced fluorescence imaging to guide total shoulder arthroplasty approach

2.0 Objectives

The purpose of this pilot study is to evaluate the feasibility of open, wide-field imaging of indocyanine green ingress and egress during total shoulder arthroplasty.

The long-term goal of this work is to use DCE-FA for the assessment of subscapularis tendon perfusion and to determine potential relationships between perfusion and patient reported outcomes and subscapularis failure.

Primary Research Question:

To what degree does the relative perfusion of the subscapularis tendon—measured using DCE-FI—change after tenotomy vs peel technique and subsequent intra-operative repair?

Hypothesis: Perfusion of the subscapularis tendon will be reduced from baseline after tenotomy and peel techniques during shoulder arthroplasty.

Secondary Question:

Does DCE-FI with indocyanine green, used in a real time, intra-operative setting, highlight technique-dependent variations in subscapularis tendon perfusion during shoulder arthroplasty?

Aim: To determine if intra-operative ICG administration during shoulder arthroplasty can be coupled with an intra-operative surgical fluorescence detection device to determine alterations in subscapularis tendon perfusion before and after repair using peel and tenotomy takedown techniques for a deltopectoral approach.

3.0 Background*

Shoulder arthroplasty is a commonly utilized and routinely successful surgery performed for management of glenohumeral joint arthritis. Upwards of 90% of primary anatomic total shoulder arthroplasty surgeries are considered successful (Lapner *et al.*, 2020). Albeit rare, complications do occur. Complications include glenoid or humeral component loosening, periprosthetic fracture, infection and rotator cuff failure. Of the four muscles that comprise the rotator cuff, the subscapularis is of particular concern in total shoulder arthroplasty surgery due to the approach used to access the glenohumeral joint. The deltopectoral approach is the standard approach used for shoulder arthroplasty and necessitates performing a subscapularis takedown in order to obtain adequate visualization of the glenohumeral joint. Three techniques to perform a subscapularis takedown are common, with an absence of consensus in the literature as to which technique is superior (Buckley *et al.*, 2014). The techniques include a subscapularis peel, a subscapularis tenotomy and a lesser tuberosity osteotomy.

PROTOCOL TITLE: Pilot feasibility study of dynamic contrast-enhanced fluorescence imaging to guide total shoulder arthroplasty approach

Each subscapularis takedown technique requires repair at the conclusion of the procedure when performing shoulder arthroplasty. Repair is crucial for proper force coupling of the shoulder to keep the humeral head implant centered on the glenoid component (Shields *et al.*, 2017). Takedown is still performed in a reverse total shoulder arthroplasty but repair is not required to maintain stability. Each takedown technique is reliant on either tendon to tendon, tendon to bone, or bone to bone interface for healing. Failure of the subscapularis tendon repair can result in pain, instability, decreased functional outcomes and ultimately the need for revision surgery (Choate *et al.*, 2018). Subscapularis tendon failure can sometimes be asymptomatic, however it can also be symptomatic and present with the aforementioned signs. Subscapularis failure rates may approach 50% in long term studies although symptomatic cases likely occur in less than 1% of total shoulder arthroplasties (Entezari *et al.*, 2020). Due to the devastating impact on patients with symptomatic subscapularis failure, there is interest in investigating which subscapularis takedown technique produces the best outcomes. Prior randomized controlled trials as well as systematic reviews have previously been conducted looking at these different takedown techniques, but demonstrated no statistically significant difference in primary endpoints of subscapularis strength at various time endpoint and no statistically significant difference in patient reported outcomes (Lapner *et al.*, 2020). These prior studies did not evaluate subscapularis perfusion post repair, adequate perfusion is necessary for healing to occur with any subscapularis takedown technique.

The takedown method of the subscapularis has previously been shown to have no statistically significant differences with regards to strength, or patient reported outcomes, however if there was a difference noted in tendon perfusion post repair this may provide rationale to choose one technique over another as improved perfusion may correlate to lower risk of repair failure. As this study aims to monitor subscapularis perfusion pre and post repair, the two techniques that the involve the tendon itself for healing will be utilized, peel and tenotomy.

The indocyanine green based DCE-FI will NOT be used to guide treatment or patient care. The data acquired using the SPY Elite or SPY PHI or EleVision will be anonymized and exported to a secure PC for additional analysis and processing. The analysis techniques will be more sophisticated than the current commercial system, and involve a correction for the patient-specific arterial input function (AIF) (Elliott *et al.*, 2020)—the cardiac and circulatory variations that can modify the time and manner in which the ICG dye arrives in the imaging field-of-view.

Indocyanine green (ICG) is a well-studied water soluble, light absorbing tracer that has been used in other capacities to help quantify tissue perfusion during

PROTOCOL TITLE: Pilot feasibility study of dynamic contrast-enhanced fluorescence imaging to guide total shoulder arthroplasty approach

surgery. ICG is able to be injected into a patient intravenously and subsequently circulate systemically while bound to albumin, quickly undergoing hepatic metabolism in just several minutes (Faybik and Hetz, 2006). The concentration of ICG in specific tissue is able to be quantified as a surrogate for tissue perfusion. ICG due to its IV administration and quick metabolism is able to help quantify perfusion in real time, such as intra-operatively (Lutken *et al.*, 2021). Systemic reviews as well as case studies, most commonly in plastic surgery, have been performed showing its utility to determine adequate or inadequate perfusion in downstream tissue in situations where microanastomoses are performed, such as with flaps (Krishnan *et al.*, 2005) and in hand surgery (Li *et al.*, 2018). Other studies have also been conducted showing the ability to use ICG as a surrogate for tissue perfusion in the achilles paratenon in humans and in rabbits who had undergone rotator cuff repair to determine tissue perfusion after different types of repair. The use of ICG imaging in orthopaedic surgery is relatively nascent, and our institution (Gitajn *et al.*, 2020) as well as other collaborators (Sepehri *et al.*, 2021) have demonstrated its promise in these applications.

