5.0 Study Intervention/Investigational Agent

5.1 Description:

This study is neither a drug nor a device trial. Patients will be administered FDA approved ICG through intravenous injection and imaged by a FDA approved surgical fluorescence imaging device (Spy Elite or SPY PHI or Medtronic EleVision) which is 0.5 meter away from the subject. Both ICG fluorescence and the imaging system have been used for routine clinical practice for many years. ICG fluorescence imaging utilizes intravenously injected ICG, which is a fluorescent dye that is FDA-approved for clinical use, illuminated with near-infrared light. The ICG dye is indirectly activated and the dynamic fluorescence due to tendon perfusion can be captured by a video rate imaging system. The subscapularis takedown technique will alternate between tenotomy and peel for every other patient taken to the operating room. There is no reason intraoperatively to choose one technique over the other and therefore this puts

PROTOCOL TITLE: Pilot feasibility study of dynamic contrast-enhanced fluorescence imaging to guide total shoulder arthroplasty approach

the patient at no added risk. If the surgeon feels that neither of these techniques are appropriate for the treatment of the patient then the patient will not be approached for enrollment.

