5.3 Dose Rationale

We plan a sample size of 10 patients in this open label prospective observational study of ICG fluorescence imaging for assessment of subscapularis tendon blood flow.

After the subscapularis tendon is visualized during the surgical approach, 0.1 mg/kg ICG will be injected intravenously. Video rate ICG fluorescence images will be acquired 20 seconds before and 4 minutes after ICG injection. This process will be repeated towards the end of the procedure after the subscapularis is repaired, but prior to skin closure.

This dose has been used to effectively assess bone perfusion in a previous study at our institution which was an IRB-approved pilot study. A total dose of 0.2 mg/kg is within the range of previous studies. Indeed, this is 10 times less than the maximum recommended dose by FDA of 2 mg/kg.

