6.0 Procedures Involved*

The research design for this study is a single cohort longitudinal study employing a consecutive sampling methodology. Eligible patients regardless of ethnicity or health

PROTOCOL TITLE: Pilot feasibility study of dynamic contrast-enhanced fluorescence imaging to guide total shoulder arthroplasty approach

status, will be identified and recruited subject to inclusion and exclusion criteria listed in section 10. Patients who meet eligibility criteria will be asked to participate in the trial. If they agree written informed consent will be obtained from the patient or their legal authorized representative. To obtain informed consent, study personnel (surgeon or research coordinator) will adhere to the following procedures: (1) present study information in a manner that is understandable to the patient; (2) discuss the study with the patient and answer any questions; (3) allow the patient an opportunity to discuss participation with their family; (4) confirm that the patient understands the risks and benefits of participating in the study and that their participation is voluntary; (5) complete the consent process and obtain signatures from the patient and research team. The process of obtaining and documenting informed consent forms will be completed in accordance with local Good Clinical Practice (GCP) recommendations.

If the research team member obtaining consent is at all unsure about the patient's ability to consent, s/he will consult with the study PI.

Patients will be randomized to undergo either a subscapularis peel or subscapularis tenotomy.

Recognizing that consent is an ongoing process, the study team will encourage the participants to ask additional questions that may arise during the course of their participation in the study.

On the surgery day, the patient will be prepared and transported to surgery as per routine at Dartmouth-Hitchcock. In the OR, patient positioning, preparation of the surgical field, and draping will follow standard practice for arthroplasty of the involved shoulder joint.

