17.0 Data Management* and Confidentiality

Data Confidentiality:

PROTOCOL TITLE: Pilot feasibility study of dynamic contrast-enhanced fluorescence imaging to guide total shoulder arthroplasty approach

The use of PHI is necessary for the purposes of this research and the PI and investigational team will protect the confidentiality of the subjects through the following actions:

Patients will be assigned a unique study identifier (*study ID*) based on the order in which they are recruited and a list of study IDs and the patients they correspond to (PHI) will be kept on a Dartmouth-Hitchcock secure server accessed by a DH laptop (the “H:/” drive). This is the only ‘key’ to matching patients and their corresponding study ID, and is only used to retrieve patient outcomes for the data analysis, and in the unlikely event that there is a reported adverse effect, to investigate the event.

A secured DH laptop will also store, in a separate document, a table containing the study date and anonymous study ID will be listed, along with any outcome information as it becomes available. This file will be kept separate from the *file containing the study ID keys*, to minimize the chance it will be *inadvertently shared with unauthorized individuals*.

The file containing the study IDs and which patients they correspond to (ID Key), will be destroyed once all outcomes have been recorded and/or the follow-up period has passed, *unless required* by the sponsor to maintain the information for an extended period of time. In that case, the ID Key will be destroyed at the earliest opportunity consistent with federal regulations.

Protected health information will not be reused or disclosed to any other person or entity, except as required by law, for authorized oversight of the research study, or for other research for which the use or disclosure of protected health information for which an authorization or opportunity to agree or object is not required by 45 CFR 164.512.

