19.0 Provisions to Protect the Privacy Interests of Subjects

All identifying data will be kept in a restricted file on a secure DHMC server that can only be accessed by the PI and research coordinators. Participant data will also be entered in the "OnCore" database, which is a secure, password protected data collection system. Individual participants are assigned a random ID number within the OnCore database.

PROTOCOL TITLE: Pilot feasibility study of dynamic contrast-enhanced fluorescence imaging to guide total shoulder arthroplasty approach

This database has restricted access, and the ability to view participant data is limited to specific members of the research team (e.g. PI and research coordinators).

No information will be disclosed to others without written permission from the patient, except:

- If necessary to protect the rights or welfare of the participant (for example, if the participant is injured and in need of emergency care); or
- If required by law.

Any discussion between the patient and the research staff will be conducted in a private location.

When the results of the research are published or discussed at conferences, no information will be included that would reveal participant identity. Authorized representatives of the D-HH IRB, Dartmouth College, and DHMC may need to review records of individual participants to ensure the accuracy of findings and to monitor the safety and welfare of study participants. The research imaging will not go into the patient's medical record and will not be used for any clinical decision-making.

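### No masking of the perfusion measurement to technique is described, and under the alternation in 5.1 a sequential study ID or study date sent with the recordings could let a reader deduce tenotomy or peel

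*Protocol*

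**What the plan says.** - **Export (3.0 Background).** Data from the imaging device "will be anonymized and exported to a secure PC for additional analysis and processing". The label on the exported files is not given.
- **Study ID (17.0 Data Management and Confidentiality).** The ID is assigned "based on the order in which they are recruited". Apart from the key that links IDs to patients, there is a second file: "a table containing the study date and anonymous study ID will be listed, along with any outcome information as it becomes available".
- **Technique (5.1 Description).** "The subscapularis takedown technique will alternate between tenotomy and peel for every other patient taken to the operating room".
- **Technique (6.0 Procedures Involved).** "Patients will be randomized to undergo either a subscapularis peel or subscapularis tenotomy". No method is given.
- **Second identifier (19.0).** "Individual participants are assigned a random ID number within the OnCore database". It is not tied to the recordings.
- **Masking.** Section 5.3 calls the work an "open label prospective observational study of ICG fluorescence imaging". Section 24.0 has departmental research staff process the data. No section describes a masked reading.
- **Use of the result.** Tenotomy versus peel stands in the primary research question and the secondary question (2.0), and the secondary objective (1.0) relates perfusion to technique. The primary endpoint (4.0) is whether the rise and fall of fluorescence can be seen.

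**The concern.** The scheme in 3.0 and 17.0 protects the patient's identity. It was not written to hide technique, and under 5.1 it may fail to do so, because operating-room order then determines technique and the study records carry order information.

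This matters only if deriving perfusion leaves room for judgement. The protocol suggests that it does. Section 4.0 leaves it to experience whether a signal is good enough to analyse, against an approximate window of 10 to 40 seconds. Region of interest is in the abbreviation list in 1.0, but no placement rule is given. A reader who knows the technique and has discretion over the region, or over which curves are usable, can move values in one group without intending to. With about five patients per technique, a few such choices could colour the comparison. Section 3.0 says that a perfusion difference might support choosing one technique over the other, so the comparison may be put to use.

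**Working it through.** The protocol gives no power, significance level or effect size behind its 10 patients, so there is no figure of its own to reproduce. The check is how much order reveals about technique.

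**Inputs.** N = 10 (1.0, 5.3, 12.0). Strict alternation by operating-room position (5.1), so 5 per technique. Study ID equals recruitment position (17.0). The reader is assumed to know which technique goes with odd and which with even positions; one known case supplies this if that case is in its expected place.

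**Step 1: study date.** I assume that the study date is the date of surgery; the protocol does not define it. Sorting by date recovers operating-room order, and alternation then gives 10/10 whatever the ID. Patients operated on the same day would be tied and not separated by date alone.

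**Step 2: study ID alone.** Technique is read correctly when the ID and the operating-room position have the same parity.

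| Relation of surgery order to recruitment order | Read correctly |
|---|---|
| Identical | 10/10 |
| One neighbouring pair swapped | 10 − 2 = 8/10 |
| Two random neighbour swaps (average) | about 6.8/10 |
| Three random neighbour swaps (average) | about 6.2/10 |
| Unrelated | about 5/10 |

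The averages come from simulation with 50,000 runs each. A second simulation let waiting time to surgery vary, with SD in units of the interval between recruits (assumed). The share read correctly was 99.6% at SD 0.25, 86% at 0.5, 62% at 1 and 53% at 2. If one of 11 recruits leaves before surgery, the parity of every later ID flips. A reader who does not know of the departure is then misled, and one who does can correct for it.

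**Step 3: randomisation as in 6.0.** If allocation is truly random, neither ID parity nor date carries information about technique. The deduction therefore rests on 5.1 being the rule applied.

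**Step 4: random code.** With a label unrelated to either order and no date, the label gives only a chance guess, 5 of 10 expected.

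**Illustration only.** The protocol names no test for the comparison. Suppose a two-sided 5% t-test with 5 per group (8 df, critical value 2.306), no true difference, and a reader effect that shifts the group difference by d SD. The noncentrality is d × √(5/2), or 0.395, 0.791 and 1.186 for d = 0.25, 0.5 and 0.75. The false-positive rates are 6.4%, 10.8% and 18.2%. The shifts are assumed; nothing in the protocol says that they occur.

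**The case against.** A reader might infer that the recordings are identified only by the sequential study ID and that this ID by itself discloses technique. The protocol does not support that. Section 3.0 names no label, and 17.0 presents the ID as a confidentiality measure without saying that image files carry it. The ID follows recruitment while alternation follows surgery; patients are enrolled in clinic beforehand (13.0, 24.0), so the two orders can differ. The date table is a separate document, and nothing says that the reader uses it. Section 6.0 says randomised. All of this stands, and it makes the point conditional.

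Three further objections carry weight. First, placement of a region on each video is an inference from an abbreviation, and reading rules could properly sit in an analysis plan that is not shown. That is fair for the detail. The numbering rule, the date table and the alternation, however, are protocol text, and coding has to be in place before the files are read. Second, the study is declared open label, so no statement about masking is contradicted. That is true, but an open-label operation does not prevent masked measurement afterwards. Third, random coding cannot hide everything. A technique effect can show only in the post-repair recording, where the repair may be visible, and research staff carry out the assessment in the operating room (15.0) as well as processing the data (24.0). This limits the gain, though the baseline of every change value comes from a pre-takedown recording, which can be masked.

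It would also go too far to read the illustrative error rates as properties of this trial, or to assume a direction of bias: the hypothesis in 2.0 is a fall after both techniques and favours neither.

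**Conclusion.** The point holds in conditional form. The protocol describes no masking of perfusion measurement to technique. If the study date or sequential ID accompanies the recordings, and if 5.1 is the rule applied, technique can be deduced: for all 10 patients from date order (given surgery dates without ties), and from the ID only as far as recruitment order matches surgery order. If 6.0 is the rule applied, order reveals nothing, but masking is still not described.

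The consequence is limited to the tenotomy-versus-peel comparison, where reader bias is possible but its size and direction cannot be determined from the protocol. Visibility of the signal, the primary endpoint, is little affected. For a feasibility pilot of 10 patients this is a worthwhile, inexpensive improvement of modest expected gain, not a flaw that undermines the study.

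**What to change.** 1. Reconcile 5.1 and 6.0 on how technique is assigned.
2. In 3.0 and 17.0, state that each exported recording is labelled with a random code unrelated to recruitment or surgery order, and that dates are removed from the files. The OnCore random ID could serve as a base only if the reader cannot look it up; the two recordings of one patient need separate codes.
3. Fix the tendon region on the frames recorded in the 20 seconds before injection, before the fluorescence curve is viewed.
4. Link codes to technique only after all perfusion values are locked.
5. State the limit: masking can hold for pre-takedown recordings, but it is partial after repair because the image, or a reader's own presence in the operating room, may reveal technique.

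The cost is a few sentences and the relabelling of about 20 files (10 patients × 2 recordings) by whoever already exports them. No extra reader is needed and clinical care does not change. The downsides are that a code list must be kept secure and that masking remains incomplete.
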